### ***Adherence to the Program***

The compliance with the intervention will be measured through the smartphone application. This will allow an assessment of the amount of treatment received, which is essential for calculating the correlation between the number of therapeutic activities performed and the variation of Cobb's angle.

### ***Gross Motor Function Level***

The gross motor function level, including the ability to walk, will be measured during the rehabilitation assessments using the Rett Syndrome Motor Evaluation Scale (RESMES – Appendix 6). This scale includes 25 items that examine motor function divided into six sections: standing, sitting, postural transfers, walking, running, and climbing / descending stairs. Sixteen items are rated on a discrete scale, ranging from 0 (indicates no or very mild impairment) and 4 (severe impairment). Nine items related to walking skills are evaluated on a discrete scale with a score from 0 to 2 where 0 indicates that the activity could always be completed by the subject and 2 that is assigned if the item cannot be carried out. The items' scores are added together, thus giving a total RESMES score (range: 0 to 82). Moreover, a score for each section can be calculated. Additionally, the RESMES was designed to be completed by the primary caregivers of the person with RTT. Comparing the total score obtained by parents and doctors revealed a high correlation and no statistically significant difference.[44] This scale was recently validated on a sample of 60 girls and women with RTT (mean age: 12 years 5 months SD: 8 years 9 months; range: 3–40 years), showing optimal agreement between the assessors and strong internal consistency (reliability coefficient = 0.96 SD = 0.18; Cronbach's alpha coefficient for the full scale = 0.95 CI 0.93–0.97).[45]

### ***Behavioral Characteristics***

The behavioral characteristics of the participants will be evaluated at T1, T2, and T3 through the administration of the Rett Syndrome Behavior Questionnaire (RSBQ - Appendix 7).[46] The RSBQ is a questionnaire created by comparing the behavioral characteristics of people with RTT with those of individuals with severe intellectual disability. The questionnaire is filled in by parents who are asked to provide an evaluation of the behavioral characteristics shown by their child at the time of completion. Because people with RTT suffer from severe physical and cognitive deficits linked to behavioral and emotional disturbances, the RSBQ includes elements describing behavioral characteristics and assessing physical capabilities, including hand function and sitting and walking skills. Other items evaluated by the questionnaire include sleep disturbances, respiratory difficulties, mood disturbances, self-harm, social skills, and stereotyped hand movements. The Chronbach's alpha for the RSBQ was high (>0.90) for the RSBQ total score and moderate (0.60–0.79) to high for all the sub-scales. The questionnaire test-retest reliability was assessed by calculating intra-class correlations between two completions of the questionnaire. Intra-class correlations

were high ( $>0.80$ ) or moderate ( $0.60-0.79$ ) for the RSBQ total score and all the subscales.[46]

### ***Caregivers' Burden***

The burden related to the implementation of the treatment will be assessed through the administration, at the end of the study, of a questionnaire to all parents, therapists, teachers, and other caregivers involved in the intervention. The items included in this questionnaire will address the burden derived from the treatment implementation, the parental satisfaction, and the intervention's perceived efficacy concerning functional skills and posture of the trunk and spine. The same questionnaire was successfully used when evaluating previous results of a few remote rehabilitation research with individuals with RTT.[38,47]

### **Statistical analysis**

The normality of each variable's distribution will be assessed using the Shapiro-Wilk normality test. The ages, amount of received physical rehabilitation interventions, scoliotic curve degrees, behavioral characteristics, and activity and gross motor functional levels obtained at T1 will be compared between the two groups to assess their comparability through Wilcoxon's signed-rank test or Student's T-test (dependent of the variable distribution characteristics). Changes that occurred in the variables of each group at T1, T2, and T3 will be evaluated with Friedman's test or with the repeated measure ANOVA (dependent on the variable distribution characteristics). Between groups comparison for each variable collected at T1, T2, and T3 and for their variations that occurred between T1 and T2 and between T2 and T3 will be conducted using the Wilcoxon's signed-rank test or Student's T-test (dependent of the variable distribution characteristics), applying an appropriate adjustment for the age and gross motor skills of the participants. Relations will be searched between variables collected at T1 and the changes in the scoliosis curve degree and motor functioning after the treatment using Spearman's rank correlation coefficient or Pearson's correlation coefficient (dependent on the variable distribution characteristics). Moreover, a relation between the compliance with the proposed program and the changes in the scoliosis curve degree and motor functioning after the treatment will be searched using the Spearman's rank correlation coefficient or Pearson's correlation coefficient (dependent on the variable distribution characteristics). The threshold for significance of the above-described analyses will be set at  $\alpha = 0.05$ . No correction for multiple comparisons will be applied.[48]

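### A Shapiro-Wilk pre-test on 10–20 values selects the method for every comparison, and no treatment-effect estimate or confidence interval is planned

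*Combined protocol and SAP*

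**What the plan says.** The Statistical analysis section opens with a normality check on every variable, whose "distribution will be assessed using the Shapiro-Wilk normality test". Every later choice refers back to it.

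- Group comparisons, at baseline and afterwards, use a Wilcoxon signed-rank test or a t-test according to the distribution. They cover every variable at all three visits and its change over each of the two periods. For Cobb angle that makes five series: T1, T2, T3 and the two changes. The same sentence promises a suitable adjustment for age and gross motor ability.
- Changes within each group "will be evaluated with Friedman's test or with the repeated measure ANOVA (dependent on the variable distribution characteristics").
- Relations with baseline variables and with compliance are examined "using the Spearman's rank correlation coefficient or Pearson's correlation coefficient (dependent on the variable distribution characteristics").

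The alpha is 0.05, and "No correction for multiple comparisons will be applied". The section does not give the level of the pre-test. It does not say whether normality is judged per group, pooled, per visit or on residuals, and no rule holds one method for one outcome. It names tests and correlation coefficients, but no mean or median difference between groups and no confidence interval. The Sample Size and Power Calculation section sets two groups of 10.

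**The concern.** A t-test addresses a difference in means; a rank test addresses a different quantity. If the data choose between them, the plan has not said what the trial estimates. At 10 to 20 values the selector is weak: it misses moderate skew most of the time and rejects some data that are normal. The check is also applied to the variable rather than to model residuals. T1 Cobb angle is cut off at 10° and 40° by eligibility while later values are not, so one outcome could change method between visits.

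The absence of an estimate and interval has more practical weight. The Importance of the Research section presents this as the first randomised attempt to establish efficacy and expects it to influence clinicians. With p-values alone, a null result in 20 girls cannot be told apart from an imprecise one.

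**Working it through.** **Inputs from the plan.** There are 10 girls per group, a natural progression of 14 ± 8° per year (the ± read as an SD), 10-month periods, an eligibility range of 10–40°, and alpha 0.05 (two-sided assumed). The plan gives no figure for the pre-test that could be reproduced. Its 10 per group does not follow from its own 14° and 12°, but this point needs only the group size.

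**Assumptions.** The pre-test level is 0.05. T1 Cobb is uniform on 10–40°. Ten-month change is 14 × 10/12 = 11.7° with SD 8 × 10/12 = 6.7°. The rank-sum test stands in for the signed-rank test, because the latter is a paired test and the groups are independent.

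**1. Reliability of the pre-test.** Simulated Shapiro-Wilk rejection rates:

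| Shape | n = 10 | n = 20 |
|---|---|---|
| Normal | 5% | 5% |
| Uniform | 8% | 20% |
| t, 3 df | 18% | 34% |
| Gamma, shape 2 | 24% | 53% |
| Lognormal, sigma 0.5 | 25% | 52% |
| Exponential | 45% | 84% |

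Moderately skewed data therefore pass about 75% of the time at n = 10. Exactly normal data, tested in each group, go to ranks in 1 − 0.95² ≈ 10% of comparisons.

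**2. Switching across the Cobb series.** With all 20 girls pooled and normal changes:

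- T1 goes to ranks in about 20% of trials, and the T1–T2 change in about 5%.
- The five series do not all get the same method in about 33% of trials.
- Without T1, the remaining four are mixed in about 17%.

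Tested per group, mixing over the five series is about 42% with normal changes and 65% with gamma-shaped changes.

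**3. Does the pre-test change significance?** This needs two things together: Shapiro-Wilk rejects, and the two tests fall on opposite sides of 0.05. At a true difference of 1.0 to 1.3 SD:

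- Normal changes: about 0.5% of trials with a pooled pre-test, about 1% per group.
- Gamma-shaped changes (shape 2): about 6–8% per group; pooling brings it lower, towards 2%.

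**4. Type I error.** The two-stage procedure gives 0.048–0.054 across the six shapes, against 0.044–0.051 for a t-test used throughout.

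**5. Precision that would go unreported.** The unadjusted 95% half-width for a group difference in change is t(0.975, 18 df) × SD × √(1/10 + 1/10):

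- SD 6.67: 2.101 × 6.67 × 0.447 = 6.3°.
- SD 8: 2.101 × 8 × 0.447 = 7.5°.

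The margin in the sample size section is 14 − 12 = 2°. A null result would therefore be compatible with effects several times that margin.

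**The case against.** The strongest reply is that little inferential harm follows from the pre-test, and that stands. Type I error is essentially unaffected, and with normal changes power at a 1 SD difference is 0.564 for the two-stage procedure against 0.566 for a t-test throughout. A reader might take the 7–8% of normal data sets in which a t-test and a rank-sum test disagree (true difference 1.0–1.3 SD) as the rate at which the pre-test decides significance. It is not: that rate ignores whether the pre-test rejects at all.

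The switching figure is also assumption-driven. It leans on T1, which is a baseline check, and on a uniform shape where the plan gives only limits. With a normal baseline, mixing over the five series is just over 20%, much of it ordinary 5% false rejections. The text can also be read as one decision per variable, which would prevent switching between visits. It does not say so, which leaves switching possible but not planned.

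It would be too strong to say that only p-values are planned, since correlation coefficients are effect measures. The gap concerns the treatment comparisons. The wide interval comes from 10 per group, not from the pre-test, and is computed without adjustment. Nor can one say how often the motor score would go to ranks, because the plan gives no distribution for it.

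Finally, the promised adjustment may be meant as a regression model. If so, the plan does not name it; the two tests it does name take no covariates.

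**Conclusion.** The point holds as a matter of an unfixed estimand and missing estimates, not of false positives. Method choice rests on a weak check with unspecified rules. Mixed methods across the Cobb series in 33% of trials (17% without T1) are illustrative values that depend on the baseline shape, the pre-test level and pooling. A reader might infer inflated type I error or results that often hinge on the pre-test. Neither is supported: type I error stays near 0.05, and significance changes in about 0.5–1% of trials unless changes are markedly skewed. The part with clear practical weight is that no treatment-effect estimate or interval is planned, together with an adjustment that the named between-group tests cannot deliver. It should be corrected before outcomes are seen.

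**What to change.** - Remove the normality test as the selector of methods.
- For the T1–T2 Cobb change, prespecify one linear model (ANCOVA) with group, T1 value, age and T1 gross motor score. Report the adjusted group difference with its model-based 95% CI whatever the distribution. Treat the other between-group comparisons likewise; where the motor score is the outcome, its T1 value already serves as the motor covariate.
- Add a permutation test that respects the block randomisation as a sensitivity check. The block size must be recorded for this, as the Study Protocol section does not give it. The permutation p-value does not rely on normality; the model-based interval still rests on the linear model.
- Name one method in advance for the within-group analyses in place of the Friedman/ANOVA choice, and one correlation coefficient. Spearman throughout is a reasonable preference but not the only defensible one.
- State that a non-significant result will be read from the interval.

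The cost is SAP wording, slightly more programming and three degrees of freedom for covariates (20 − 5 = 15 residual, against 18 unadjusted). No new data, visits or participants are needed.

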## **Study Protocol**

The participants' parents will receive an information sheet regarding the study and informed consent for participation and collection of video materials at the recruitment. A reference telephone number and an e-mail address will be provided to be contacted in case they would like further information or would like to communicate the exit from the study. The eligibility of the candidates will be assessed at the time of recruitment (T1) through an initial neurological or physiatrist evaluation. At the same time, each participant will undergo a rehabilitation evaluation to collect the outcome measures (see section "Data collection") and create an individualized intervention plan specific to the participant's scoliosis, functional abilities, and parental/educational setting's availability. During the evaluation, the postural needs of the participants will also be identified, and a qualified technician will build or adjust the positioning devices, making them suitable for each intervention plan. Using block randomization, participating girls will be randomly divided into treatment (Group 1) or delayed treatment (Group 2) groups. Participants in Group 1 will begin carrying out the rehabilitation program immediately after the first assessment session (T1). Each program will require the daily performance of different postures and therapeutic activities at the girls' educational facilities and homes, based on the availability of families, for a duration of 10 months. Specific strategies that will be implemented will include maintaining asymmetrical postures that oppose the scoliosis curve during activities and exercises in sitting, standing, and walking positions (according to each participant's functional abilities). These strategies refer to a hypercorrective postural positioning of scoliosis. In addition, activities involving weight bearing on the lower limbs, such as walking and standing for at least two hours a day, will be encouraged, and passive stretching and spinal mobilization exercises will be conducted.

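### The plan names a paired test (Wilcoxon's signed-rank) for comparing two independent randomised groups, so in the non-normal branch the p-value depends on an arbitrary pairing of unrelated girls

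*Combined protocol and SAP*

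**What the plan says.** The Study Protocol section sets up two parallel arms: "Using block randomization, participating girls will be randomly divided into treatment (Group 1) or delayed treatment (Group 2) groups". It describes no matching of girls across arms.

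The Statistical analysis section then names the signed-rank test in two places, both for comparisons between the arms:

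- **Baseline.** Age, prior rehabilitation, curve size, behaviour and motor level at T1 "will be compared between the two groups to assess their comparability through Wilcoxon's signed-rank test or Student's T-test".
- **Outcomes.** The scope is given as "Between groups comparison for each variable collected at T1, T2, and T3 and for their variations that occurred between T1 and T2", to which the sentence adds the change over the second period. The choice of test for all of these is the same as at baseline: the analysis "will be conducted using the Wilcoxon's signed-rank test or Student's T-test".

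The second sentence covers change in Cobb angle, so it contains the randomised efficacy comparison.

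The choice between the two tests depends on distribution: "The normality of each variable's distribution will be assessed using the Shapiro-Wilk normality test". The signed-rank test is the non-normal branch. Change within a group has its own methods: "Changes that occurred in the variables of each group at T1, T2, and T3 will be evaluated with Friedman's test", or repeated-measures ANOVA. The rank-sum (Mann-Whitney) test is not named anywhere, and the t-test is not identified as the independent-samples form.

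**The concern.** The signed-rank test ranks differences within pairs, such as one girl at two times or two deliberately matched girls. Group 1 and Group 2 contain different girls with no link between them, so those differences do not exist until someone creates them. Software asked for this test subtracts row 1 of one column from row 1 of the other, and so on. The p-value then reflects the sort order of the file as well as the data.

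Two things are at stake whenever normality is rejected:

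- The main efficacy p-value is not reproducible. Two analysts with the same data in a different order can reach opposite conclusions.
- The test needs equal numbers. If one girl leaves, 9 against 10 cannot be paired, and one girl must be discarded under a rule that the plan does not give. With 10 per group that is a real loss.

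Block randomisation does not rescue the test. It balances numbers over time but does not make pairs, and the plan does not say that blocks enter the analysis.

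**Working it through.** **Inputs.** Two groups of 10, SD 8° and mean progression 14° per year come from Sample Size and Power Calculation. The 10-month intervention comes from Study Protocol, and α = 0.05 from Statistical analysis. Three inputs are assumptions: two-sided tests, normal data, and the annual SD applied to a 10-month change. Expected 10-month progression is 14 × 10/12 = 11.7°. Halving it gives the 5.8° used below as an illustrative effect.

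**Step 1: can the sentences be read as a within-girl test?** No. Both say that the comparison is between groups, and within-group change is assigned to Friedman's test or repeated-measures ANOVA.

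**Step 2: one data set, two row orders.** Take 10 values per group at the normal quantiles (i − 0.5)/10, SD 8, with a group difference of 8° (7.99° after a 0.01° shift to avoid ties). Two groups of 10 can be paired in 10! = 3,628,800 ways.

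- *Both columns sorted the same way.* All ten differences are positive. The p-value is 2 × 1/1024 = 0.002.
- *One column reversed.* The differences are 7.99 + 16z for the ten quantiles z: −18.3, −8.6, −2.8, 1.8, 6.0, 10.0, 14.2, 18.8, 24.6, 34.3. The negative values hold ranks 7, 4 and 2 of absolute size, which sum to 13. Of the 1,024 sign patterns, 82 give a sum of 13 or less, so p = 2 × 82/1024 = 0.160.
- *Rank-sum test on the same 20 values.* p = 0.043 in any order.

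Over 20,000 random pairings of these values, the signed-rank p ran from 0.002 to 0.557 (median 0.064) and was below 0.05 in 44% of pairings. At a 10° difference the rank-sum p is 0.019. The signed-rank p ran from 0.002 to 0.232 and was below 0.05 in 87% of pairings.

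**Step 3: how often the conclusion changes.** Each simulated trial has two independent groups of 10. The exact signed-rank test is applied after random pairing. The second and third columns show ranges over repeated runs of 600 to 1,500 trials per effect.

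| True difference | Both significant and non-significant results among 20 pairings | Median p-value spread over 20 pairings | Two arbitrary pairings disagree |
|---|---|---|---|
| 0° | 15–16% | 0.45–0.46 | about 4–5% |
| 5.8° | 45–49% | 0.26–0.29 | about 14–16% |
| 8° | 50–53% | – | – |
| 10° | – | – | about 16% |
| 10.6° | 45–46% | – | about 15% |

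**Step 4: error rate and power (20,000 trials).**

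| True difference | Signed-rank, arbitrary pairing | Rank-sum | t-test |
|---|---|---|---|
| 0° | 4.8% | 4.5% | 5.1% |
| 10° | 68% | 71% | 75% |

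**The case against.** The strongest reply is that this is a naming slip. The sentences speak of comparing groups, set the test beside Student's t-test and treat within-group change separately, so the authors plausibly meant Wilcoxon's rank-sum test. That may be so, but the document does not say it. The paired test is named both times, and an analyst who follows the plan would run the wrong procedure.

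Four further points limit the size of the harm:

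- The 20-pairing figure rises with the number of pairings tried. An analyst uses one file order, so disagreement between two pairings, about 4% to 16%, is the fairer measure of what would happen in practice.
- Only the non-normal branch is affected, yet the simulated data are normal. If Shapiro-Wilk is applied at 0.05 in each group (the plan does not say how), at least one group is rejected in about 1 − 0.95² = 10% of such trials. Counting only those trials, changes of conclusion at 5.8° fall to about 5% of all trials on the 20-pairing measure and 1.5% on the two-pairing measure. Real Cobb changes and scale scores may be less normal, which would send more comparisons to this test.
- With the pairing fixed before outcomes are seen, the false-positive rate stays near 5% and the power loss is a few points. There is no protection if the order is settled afterwards.
- Neither the rank-sum test nor the t-test can carry the planned adjustment for age and gross motor skills. That is correct, but it is a separate gap that this correction does not close.

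These points reduce the expected damage. They do not make the named test valid for unpaired groups.

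**Conclusion.** The plan is wrong as written. It specifies a paired test for two independent groups, both at baseline and in the sentence that covers the efficacy comparison, and it provides no pairs.

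Where the non-normal branch applies, the p-value is not determined by the data. Two arbitrary pairings disagree on significance in roughly one trial in seven at effects of 5.8° to 10.6°, and in about one in twenty-two with no effect. One example data set gives p = 0.002 or p = 0.160 according to row order, against a single rank-sum p of 0.043. The problem is reproducibility and an open analytic choice, together with the forced discarding of girls if the groups become unequal. Type I error is not inflated when the pairing is set blind.

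The sizes rest on 10 per group, SD 8°, normal data and two-sided testing. The existence of the error rests on none of these.

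**What to change.** In both sentences of the Statistical analysis section, replace the signed-rank test with the *Wilcoxon rank-sum (Mann-Whitney) test*, and write *independent-samples t-test* in place of the unqualified Student's t-test. Keep the signed-rank test, if it is wanted, only for paired contrasts within a group, such as Group 2's change during waiting against its change during treatment.

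The cost is two wording changes before the data are analysed, with no effect on recruitment, visits or data collection. The covariate-adjusted model for age and gross motor skills needs its own specification, but this correction does not depend on it.

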## **Abstract**

**Background:** Scoliosis is the most common orthopedic comorbidity in Rett syndrome (RTT), with a prevalence of 94% and a mean curve progression of 14-21° Cobb annually. A scoliosis prevention intervention based on daily activity programs was proposed for people with RTT within uncontrolled study designs.

**Aim:** The current study aims to evaluate the effectiveness of a home-based activity program carried out during daily life to slow the progression of scoliosis in girls with RTT.

**Ethics:** The proposal was approved by Ariel university IRB. All participants' parents will sign informed consent forms.

**Participants:** Twenty Italian girls aged between six and 16 years with a genetically confirmed classic RTT and scoliosis at a severity level between 10° and 40° Cobb will be recruited and randomly divided into two groups (immediate intervention – Group 1; wait-list-intervention – Group 2). Both groups will follow the same 10-month intervention program, 10 months apart.

**Outcome measures:** Participants' scoliosis Cobb's angle, motor functioning, and behavioral characteristics will be assessed three times.

**Procedure:** The interventions will comprise daily home-based activity programs carried out by participants' caregivers within everyday living environments. An expert therapist will remotely supervise each program through an ad hoc developed smartphone application.

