## **Sample Size and Power Calculation**

The information available in the literature suggests that the Cobb angle in RTT typically increases by approximately  $14 \pm 8^\circ$  Cobb per year. Based on these data, an alpha of 0.05 and a beta of 0.8, we estimate that for this study, the researchers will need a sample size including two groups of 10 subjects and that statistical significance will be achieved if both groups of participants will show an average increase in the scoliotic curve of less than  $12^\circ$  Cobb after the implementation of the proposed program.

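### Baseline significance tests with 10 girls per group cannot show comparability, and T1 Cobb is missing from the adjustment, so the T2 and T3 Cobb level comparisons carry any chance T1 gap

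*Combined protocol and SAP*

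**What the plan says.** Under Statistical analysis, the T1 values of age, amount of rehabilitation, Cobb angle, behaviour and motor level "will be compared between the two groups to assess their comparability", by a t-test or a Wilcoxon test depending on normality. The section closes with "The threshold for significance of the above-described analyses will be set at" 0.05, without multiplicity correction. It gives no size of difference that would count as comparable, and no consequence of the result.

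The same section then compares the groups on two things: each variable's level at T1, T2 and T3, and its change from T1 to T2 and from T2 to T3. Both are adjusted for age and gross motor skills. T1 Cobb is not in that list.

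The Sample Size section plans "a sample size including two groups of 10 subjects". Study Protocol describes block randomisation and mentions no stratification. The Abstract sets the eligibility window: "scoliosis at a severity level between 10° and 40° Cobb will be recruited".

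**The concern.** Calling two groups comparable is a claim of similarity, and a non-significant test with 10 per group is very weak support for it. After a fair randomisation the null hypothesis of each baseline test is true by construction. A significant result is therefore a chance event, and a non-significant one does not show that these 20 girls are alike.

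T1 Cobb matters most. It is the starting value of the main outcome, and nothing else in the plan balances it or adjusts the level comparisons for it. If the T1 test is read as clearance, a real T1 gap in the allocation obtained passes unremarked into the T2 and T3 levels and can be mistaken for a programme effect, or can hide one. The level comparison also leaves between-girl variation in starting angle in its error term, although T1 Cobb is collected anyway.

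**Working it through.** **Inputs from the documents.** 10 per group; alpha 0.05 (two-sided assumed, as the plan does not say); T1 Cobb between 10° and 40°; progression 14 ± 8° per year; 10 months per period. The plan gives no power or detectable difference for the baseline tests, so it has no figure of its own to reproduce here.

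**Assumptions.** The documents give no SD for T1 Cobb. A uniform spread over the window gives SD = 30/√12 = 8.7°; a range of 5–10° is shown where it matters. Progression is scaled to 10 months (mean 14 × 10/12 = 11.7°, SD 8 × 10/12 = 6.7°) and taken as independent of T1 Cobb.

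**1. What the T1 test can flag.** The smallest significant observed gap, in pooled SDs, is t(0.975; 18 df) × √(2/10) = 2.101 × 0.447 = 0.94. In degrees this is 4.7 at SD 5, 8.1 at SD 8.7 and 9.4 at SD 10. An observed gap of 0.5 SD gives t = 0.5/0.447 = 1.12 and p = 0.28.

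**2. Miss rates against a true difference (noncentral t, 10 per group).**

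| True difference | Power | Missed |
|---|---|---|
| 0.5 SD | 18.5% | 81.5% |
| 0.8 SD | 39.5% | 60.5% |
| 1.0 SD | 56.2% | 43.8% |

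These are for the t-test branch; a rank-sum test misses a 0.5-SD difference about 84% of the time. (The Wilcoxon test that the plan names is the signed-rank test, which is for paired data.)

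**3. How often a chance gap goes unflagged.** Simulation of 200,000 randomisations with T1 Cobb uniform on 10–40°: 27% have a T1 gap of at least 4.3° (half an SD). Of those, 80% are non-significant, which is 21% of all trials.

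**4. What that does to the planned comparisons, with no programme effect.**

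| Trials considered | T2 level test rejects |
|---|---|
| All | 5.0% |
| T1 test non-significant | 3.0% |
| Unflagged T1 gap ≥ 4.3° (21% of trials) | about 10% |
| Unflagged T1 gap ≥ 6° (7% of trials) | about 16% |

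In the trials with an unflagged gap of at least 4.3°, mean T2 levels differ by 5.7° on average. In those same trials the T1–T2 change test rejects in 5.0%, and an ANCOVA of T2 Cobb on group and T1 Cobb rejects in about 5%.

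**5. Precision.** The SD of the T2 level is √(8.7² + 6.7²) ≈ 10.9°. Conditional on T1 Cobb it is 6.7°. The variance ratio is (10.9/6.7)² ≈ 2.6, so the unadjusted level comparison has more than twice the error variance it needs.

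**The case against.** **The change comparison is also planned.** This is the strongest objection, and it stands. The same sentence compares changes from T1, the outcome is named as progression, and the sample-size section speaks of an average increase. Subtracting T1 removes a pure level gap, as step 4 shows. Only dependence of progression on the starting angle could leave some exposure. The cohort figure in the Introduction (0.438 per year on the square-root scale) implies about 3.0° per year from 10° (2 × 0.438 × √10 + 0.438²) and 5.7° from 40°.

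**Overall error.** A reader might infer from the 10% and 16% that the trial's false-positive rate is inflated. It is not: the level test rejects in 5.0% of all trials, and in 3.0% of those that pass the T1 test. The higher figures describe a selected minority of allocations. They also ignore the adjustment for age and gross motor level, which would absorb part of a T1 gap if those variables correlate with Cobb.

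**Size against the planned effect.** A reader might set an unflagged T1 gap against a planned effect of 14 − 12 = 2°. The documents do not support that. The sample-size section states no between-group difference: its 12° threshold applies to both groups after the programme, and the 14° is per year while each period lasts 10 months.

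**No decision depends on the tests.** This is also correct. The plan does not say that p > 0.05 means comparable, and the adjustment applies whatever the tests show. What remains is that a significance test is the only criterion offered for comparability, and that T1 Cobb is outside the adjustment.

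**Conclusion.** The point holds in limited form. The baseline tests cannot do the job the plan gives them: with 10 per group a T1 gap must reach about 0.94 SD before it is flagged, and a true 0.5-SD difference is missed 81% of the time. Neither figure depends on the T1 Cobb SD.

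The consequence falls on the T2 and T3 Cobb level comparisons, which are not conditioned on T1 Cobb. It takes two forms: a misleading result in particular allocations (about 10% false rejection at T2 when an unflagged T1 gap is at least 4.3°) and a larger residual SD than necessary (about 10.9° against 6.7°). Both figures rest on the assumed uniform T1 distribution and on progression independent of T1. Unconditional type I error is unaffected, and the T1–T2 change comparison is largely protected. The change is worth making because it needs no further data.

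**What to change.** In the Statistical analysis section:

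- Delete the between-group tests of T1 variables and the stated purpose of judging comparability by them.
- Report T1 means, SDs and standardised differences by group, without p-values.
- Add T1 Cobb to the adjustment set. State that T2 Cobb, and likewise T3 Cobb, is compared between groups by ANCOVA with T1 Cobb, age and gross motor level as covariates, whatever the baseline table shows.

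The cost is one residual degree of freedom (with 20 girls, two groups and three covariates, 15 remain instead of 16) and a little analysis work. No extra girls, visits or radiographs are needed. The plan gives up only the statement that the groups did not differ significantly at T1.
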